9.1.1. Adverse Events Leading to Discontinuation of Study Drug

A summary of incidence rates (frequencies and percentages) of TEAEs leading to discontinuation of study drug, overall and by treatment group, SOC, and preferred term will be prepared for the Safety population. No inferential statistical tests will be performed.

A data listing of AEs leading to discontinuation of study drug will also be provided, displaying details of the event(s) captured on the CRF.

9.1.2. Deaths and Serious Adverse Events

Serious adverse events will be displayed in a separate by-subject listing.

9.2. Clinical Laboratory Evaluations

Descriptive summaries of observed values and change from baseline values will be presented for continuous hematology, chemistry (also including prolactin and thyroid function parameters) for each treatment group and overall subjects at each study visit. Urinalysis results will be listed.

Laboratory values that are outside the normal range will also be flagged in the data listings and presented with the corresponding normal ranges. Any out-of-range hematology or clinical chemistry values that are identified by the investigator as being clinically significant will also be shown in a separate data listing.

Urine drug screen and pregnancy test results will be listed.

9.3. Vital Signs

Descriptive summaries of observed values and changes from baseline will be calculated for systolic blood pressure (mmHg), diastolic blood pressure (mmHg), heart rate (beats/min), respiratory rate (breaths/min), and temperature (°C), overall, by treatment group, and by study visit.

9.4. Electrocardiograms

The number and percentage of subjects with normal and abnormal 12-lead ECG findings will be summarized overall and by treatment group at each study visit. Abnormal results will be grouped as clinically significant and not clinically significant.

Descriptive summaries for the observed results and change from baseline will be presented for 12-lead ECG measures of RR interval (msec), PR interval (msec), QRS interval (msec), and heart rate (bpm) for each treatment group and overall subjects at each study visit. If triplicate reads are taken, the mean of the reads will serve as the observed value at the specific visit.

A comparison of QT results will be presented. Summary statistics for baseline values at Visit 1 (Screening) and Visit 6 will be displayed overall and by treatment group for QT interval (msec) and QT interval corrected for heart rate using Fridericia's formula (QTcF) (msec). In addition, the number and percent of subjects in each treatment group who experienced a change >30 msec or a change >60 msec will be presented.

9.5. Physical Examination

Physical examination findings will be listed. Abnormal results and clinically significant abnormal results will be flagged.

9.6. Concomitant Medication

The number and percentage of subjects taking each concomitant medication will be summarized by treatment group and overall subjects. Medications will be classified by ATC Class Level 2 and preferred term.

9.7. Columbia-Suicide Severity Rating Scale (C-SSRS)

The number and percentage of subjects reporting "Yes" for any of the 5 suicidal ideation questions (Categories 1 to 5) or any of the 5 suicidal behavior questions (Categories 6 to 10) will be displayed for each treatment group and overall subjects, along with the number and percentage reporting suicidal ideation OR behavior (Categories 1 to 10). The number and percentage of subjects with treatment emergent suicidal ideation, treatment emergent suicidal behavior, and treatment emergent suicidal ideation or behavior as defined in Section 6.1.7.9 will also be presented.

9.8. Montgomery-Asberg Depression Rating Scale (MADRS)

For each subject and visit, MADRS total scores will be derived as described in Section 6.1.7.8. Summaries of MADRS total scores and changes from baseline will be presented by visit, overall and by treatment group.

9.9. Physician Withdrawal Checklist (PWC-20)

Physician Withdrawal Checklist total scores and proportion of subjects with at least one symptom will be derived as described in Section 6.1.7.10. Mean PWC-20 total score will be compared between PH94B- and placebo-treated subjects using a 2-sample t-test. Summaries of PWC-20 total scores and frequency and percentage of subjects with withdrawal symptoms will be presented overall and by treatment group. The difference in total score means, SE of the difference, p-value and 95% confidence interval will be displayed.

10. Other Planned Analysis

No additional analyses are prospectively planned for this study.

10.1. Coronavirus 2019 (COVID-19) Impact

The SARS-CoV-2 virus and variants may still be a threat and safety precautions may still be in place during study enrollment. To assess the impact of the COVID-19 pandemic on study procedures, study staff will complete the COVID-19 Impact questionnaire. Should a study visit be affected by COVID-19, study staff will record how the visit was affected (missed, abbreviated, delayed, performed remotely, or otherwise deviating from the planned format in the protocol) and which procedures were impacted. All COVID-19 protocol deviations will be provided in a separate listing. This listing will include the subjects, affected visits, and affected assessments.

11. Changes from Planned Analysis

Study staff will complete the Coronavirus 2019 (COVID-19) Impact questionnaire to assess the impact of the COVID-19 pandemic on study procedures. The COVID-19 Impact questionnaire is described in Section 10.1. All COVID-19 protocol deviations will be provided in a separate listing.

The ADNMs subscales exploratory endpoints analysis will not be completed as part of this SAP.

Physical examination and urinalysis results will not be summarized using descriptive statistics but will be listed.

The treatment failure sensitivity analysis will be replaced with a control-case sensitivity analysis that imputes the mean change from baseline to Week 6 in HAM-A total scores from the placebo group for missing change from baseline responses. This approach accounts for the potential for a

high placebo response.

12. References

- ASA. (2018) Ethical Guidelines for Statistical Practice. Prepared by the Committee on Professional Ethics, April 2018. <http://www.amstat.org/about/ethicalguidelines.cfm>
- Carpenter JR and Kenward MG. *Multiple Imputation and its Application (Statistics in Practice)*. Chichester, West Sussex, UK: John Wiley & Sons; 2013.
- Graham JW, and Olchowski AE, Gilreath TD. (2007) “How Many Imputations are Really Needed? Some Practical Clarifications of Multiple Imputation Theory.” *Prev Sci.* 2007;8(3): 206-213.
- ICH (1998). ICH Harmonised Tripartite Guideline. Statistical Principles for Clinical Trials E9; 1998. https://database.ich.org/sites/default/files/E9_Guideline.pdf
- Little R and Rubin D. (1987). *Statistical Analysis with Missing Data*, New York: Wiley.
- RSS. (2014) *The Royal Statistical Society: Code of Conduct*, 2014. <https://rss.org.uk/about/policy-and-guidelines/code-of-conduct/>.

13. Tables and Listings

All listings and tables will have a header showing the sponsor company name and protocol and a footer showing the version of SAS, the file name and path, and the source of the data (e.g., listing number).

The following are planned summary tables for protocol number PH94B-CL029. The table numbers and page numbers are place holders only and will be determined when the tables are produced.

13.1. Demographic Data

Table 5: Demographic Data Summary Tables

Table Number	Population	Table Title/Summary
14.1 Demographic Data Summary Tables		
Table 14.1.1	All Subjects	Subject Disposition
Table 14.1.2	Safety	Protocol Deviations and Violations
Table 14.1.3.1	Safety	Demographics and Baseline Characteristics
Table 14.1.3.2	ITT	Demographics and Baseline Characteristics
Table 14.1.4	Safety	Medical and Psychiatric History by System Organ Class and Preferred Term

Table Number	Population	Table Title/Summary
Table 14.1.5	Safety	Prior Medications by ATC Class Level 2 and Preferred Term
Table 14.1.6	Safety	Exposure to Study Drug

13.2. Efficacy Data

Table 6: Efficacy Data

Table Number	Population	Table Title / Summary
Table 14.2. Efficacy Tables		
Table 14.2.1.1	ITT	ANCOVA Change from Baseline in HAM-A Total Scores by Visit – Primary Analysis
Table 14.2.1.2	ITT	ANCOVA Change from Baseline in HAM-A Total Scores by Visit – Sensitivity Analysis Using Complete Cases
Table 14.2.1.3	ITT	ANCOVA Change from Baseline in HAM-A Total Scores by Visit – Control-Case Sensitivity Analysis
Table 14.2.2.1	ITT	Analysis of the Proportion CGI-I Responders – Secondary Analysis
Table 14.2.3.1	ITT	Analysis of the Proportion PGI-C Responders – Secondary Analysis
Table 14.2.4.1	ITT	ANCOVA Change from Baseline in ADNMM Total Scores by Visit – Secondary Analysis
Table 14.2.5.1	ITT	ANCOVA Change from Baseline in IADQ Total Scores by Visit – Secondary Analysis
Table 14.2.6.1	ITT	ANCOVA Change from Baseline in HAM-A Total Scores by Visit – Exploratory Endpoint

13.3. Safety Data

Table 7: Safety Data

Table Number	Population	Table Title / Summary
14.3.1 Displays of Adverse Events		
Table 14.3.1.1	Safety	Overall Summary of Treatment Emergent Adverse Events
Table 14.3.1.2.1	Safety	Treatment Emergent Adverse Events by System Organ Class and Preferred Term
Table 14.3.1.2.2	Safety	Treatment Emergent Adverse Events by Preferred Term
Table 14.3.1.3	Safety	Treatment Emergent Adverse Events by System Organ Class, Preferred Term, and Maximum Severity
Table 14.3.1.4	Safety	Treatment Emergent Adverse Events by System Organ Class, Preferred Term, and Maximum Relationship to Study Drug

Table Number	Population	Table Title / Summary
14.3.2 Summary of Deaths, Other Serious and Significant Adverse Events		
Table 14.3.2.1	Safety	Treatment Emergent Adverse Events Leading to Discontinuation of Study Drug by System Organ Class and Preferred Term
14.3.3 Narratives of Deaths, Other Serious and Certain Other Significant Adverse Events		
Table 14.3.3.1	Safety	Subject Listing of Serious Adverse Events
Table 14.3.3.2	Safety	Subject Listing of Adverse Events Leading to Discontinuation of Study Drug
14.3.4 Abnormal Laboratory Values		
Table 14.3.4.1	Safety	Subject Listing of Clinically Significant Abnormal Laboratory Values: Hematology
Table 14.3.4.2	Safety	Subject Listing of Clinically Significant Abnormal Laboratory Values: Clinical Chemistry
14.3.5 Laboratory Data Summary Tables		
Table 14.3.5.1	Safety	Hematology: Observed Results and Change from Baseline by Visit
Table 14.3.5.2	Safety	Clinical Chemistry and Thyroid: Observed Results and Change from Baseline by Visit

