10.3.2.1 Clinical Laboratory Safety Assessments

10.3.2.1.1 Clinical Laboratory Tests to be Performed

Samples for the following laboratory tests will be collected at the time points specified in the schedule of events (Table 2-1).

All laboratory tests will be performed on site during the study, and include the following:

Chemistry Panel:	alanine aminotransferase, aspartate aminotransferase, albumin, calcium, chloride, alkaline phosphatase, bicarbonate, cholesterol, creatine kinase, creatinine, direct bilirubin, lactate dehydrogenase, magnesium, globulin, glucose, gamma-glutamyl transferase, indirect bilirubin, phosphorous, potassium, sodium, total bilirubin, total protein, triglycerides, urea nitrogen, uric acid
Hematology/ Hemogram Panel:	hematocrit, hemoglobin, mean corpuscular hemoglobin, mean corpuscular concentration, mean corpuscular volume, platelets, red blood cell count, white blood cell count, red blood cell morphology
Hematology Differential Panel:	basophils, eosinophils, lymphocytes, monocytes, neutrophils
Urinalysis macroscopic panel:	bilirubin, blood, clarity, color, glucose, ketones, leucocyte esterase, nitrite, pH, protein, specific gravity, urobilinogen
Urine Pregnancy Test:	for all female subjects of childbearing potential
Urine Drug Screen:	tricyclic antidepressants, opiates, cocaine, benzodiazepines, amphetamines, barbiturates, cannabinoids, methadone, methamphetamine, phencyclidine, propoxyphene, buprenorphine, ecstasy, oxycodone

- Other:
 - prolactin
 - thyroid stimulating hormone
 - free thyroxine (T4) (if thyroid stimulating hormone is above the upper or below the lower normal limits, then free thyroxine will automatically be performed)

The local laboratory should be used for any unscheduled and follow-up labs, if needed. This includes any confirmatory pregnancy or drug screens for positive urine tests. Additional urine and blood samples may be collected for further evaluation of safety as warranted by the Investigator's judgment.

Results and reports from the local laboratory should be filed with the source documents for each subject. The local laboratory will provide results to the study site staff as soon as they are available and will be provided to sponsor or designated data manager within agreed timelines.

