Any laboratory value outside the normal range will be flagged for the attention of the Investigator, who must indicate whether the value is of clinical significance. If the result of any laboratory test performed during Screening (Visit 1) or Baseline (Visit 2) is clinically significant, the subject should not be randomized at Visit 2. However, any abnormal result may be repeated to confirm the finding before excluding the subject from potential inclusion in the study. In addition, subjects should be excluded if they have any other abnormal laboratory test at Screening (Visit 1) that, in the Investigator's judgment, is medically significant in that it would impact the safety of the subject, the conduct of the study, or the interpretation of the study results.

Follow-up/unscheduled laboratory tests may be performed on clinically significant abnormalities as indicated by the Investigator. Unscheduled laboratory tests may be repeated at any time at the discretion of the Investigator for appropriate medical care.

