6.1.7. Derived Variables

6.1.7.1. General

- **Age:** Age will be calculated as the integer difference in years between the subject's date of informed consent and the date of birth.

- **Baseline:** The last observation prior to the first dose of study drug. See Section 6.1.1 for more detail.
- **Change from baseline:** The value at the target time point minus the value at baseline.
- **Prior and concomitant medications:** All medications taken in the month prior to Visit 1 (Screening) or in the time interval between Visit 1 (Screening) and Visit 2 (Baseline) will be considered prior medications, whether or not they were stopped before Visit 2 (Baseline). Any medications continuing or starting after Visit 2 (Baseline) will be considered concomitant. If a medication starts before Visit 2 (Baseline) and continues after Visit 2 (Baseline) it will be considered both prior and concomitant.
- **Study day:** For analysis purposes, Study day is calculated relative to the date of first dose of study drug.
- **Treatment emergent adverse event (TEAE):** Treatment emergent adverse events are defined as 1) AEs with onset at the time of or following the start of treatment with IP through Visit 7 (Follow-Up) or 2) AEs starting prior to the start of treatment but increasing in severity or relationship at the time of, or following, the start of treatment with IP through Visit 7 (Follow-Up).
- **Total vial weight dispensed (grams):** Subjects will be dispensed 2 vials of the appropriate IP at Visits 2, 3, 4, and 5. The vial weights will be recorded prior to dispensation. For each subject and visit where vials were dispensed, calculate the total vial weight dispensed as the sum of the weight of the 2 vials prior to dispensation. If a subject is missing a weight for one or both vials at a visit, then the total vial weight dispensed at that visit will be set to missing.
- **Total vial weight returned (grams):** At Visits 3, 4, 5, and 6, subjects will return the IP vials that were dispensed at the previous visit. The weights of the returned vials will be recorded. For each subject and visit where vials were returned, calculate the total vial weight returned as the sum of the weight of the 2 vials returned. If a subject is missing a weight for one or both vials at a visit, then the total vial weight returned at that visit will be set to missing.

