Subject Listing of Clinically Significant Abnormal Laboratory Values: Clinical Chemistry
Safety Population

Same as shell 14.3.4.1.

Table 14.3.5.1
Hematology: Observed Results and Change from Baseline by Visit
Safety Population

Parameter (unit) Study Visit [1] Statistics	PH94B (N=XX)		Placebo (N=XX)		Overall (N=XXX)	
	Observed	CFB	Observed	CFB	Observed	CFB
Parameter (unit)						
Visit 1 (Screening)						
n	XX		XX		XXX	
Mean (SD)	XXX.X (XX.XX)		XXX.X (XX.XX)		XXX.X (XX.XX)	
Median	XXX.X		XXX.X		XXX.X	
Min, Max	XXX, XXX		XXX, XXX		XXX, XXX	
Visit 2						
n	XX		XX		XXX	
Mean (SD)	XXX.X (XX.XX)		XXX.X (XX.XX)		XXX.X (XX.XX)	
Median	XXX.X		XXX.X		XXX.X	
Min, Max	XXX, XXX		XXX, XXX		XXX, XXX	
Baseline						
n	XX		XX		XXX	
Mean (SD)	XXX.X (XX.XX)		XXX.X (XX.XX)		XXX.X (XX.XX)	
Median	XXX.X		XXX.X		XXX.X	
Min, Max	XXX, XXX		XXX, XXX		XXX, XXX	
Visit 6 (End of Treatment/ Early Termination)						
n	XX	XX	XX	XX	XXX	XX
Mean (SD)	XXX.X (XX.XX)	XXX.X (XX.XX)	XXX.X (XX.XX)	XXX.X (XX.XX)	XXX.X (XX.XX)	XXX.X (XX.XX)
Median	XXX.X	XXX.X	XXX.X	XXX.X	XXX.X	XXX.X
Min, Max	XXX, XXX	XXX, XXX	XXX, XXX	XXX, XXX	XXX, XXX	XXX, XXX

Abbreviations: CFB = change from baseline, SD = standard deviation.

Note: Baseline is defined as the last non-missing assessment before receiving the first dose of study drug. Change from baseline is calculated as result – baseline result.

[1] Visit 6 (End of Treatment/Early Termination) includes data from subjects who either completed Visit 6 (End of Treatment) or who discontinued from the study and completed an early termination visit.

Reference Listing: 16.2.8.1

Table 14.3.5.2
Clinical Chemistry and Thyroid: Observed Results and Change from Baseline by Visit
Safety Population

Same as shell 14.3.5.1; Programming Note: Update Reference Listing to Listing 16.2.8.2.

Table 14.3.6.1
Vital Signs: Observed Results and Change from Baseline by Visit
Safety Population

Same shell as 14.3.5.1; Programming note: Summaries should be presented for the following visits: Visit 1 (Screening), Visit 2, Baseline, Visit 3, Visit 4, Visit 5, Visit 6 (End of Treatment/Early Termination), Visit 7 (Follow-Up). Parameters include systolic blood pressure (mmHg), diastolic blood pressure (mmHg), heart rate (beats/min), respiratory rate (breaths/min), and temperature (°C). Update Reference Listing to Listing 16.2.9.1.

[figure not shown]

Table 14.3.6.2.1
 12-Lead Electrocardiogram: Summary of Interpretation by Visit
 Safety Population

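### Free T4 is a reflex test, so its planned change-from-baseline summary cannot include anyone whose TSH first goes out of range on treatment, and its Visit 6 mean covers only TSH-selected subjects

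*SAP*

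**What the plan says.** Protocol 10.3.2.1.1 lists prolactin and TSH without condition. Free T4 is conditional: "if thyroid stimulating hormone is above the upper or below the lower normal limits, then free thyroxine will automatically be performed". TSH and free T4 are the only thyroid tests named there.

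SAP 9.2 plans observed and change-from-baseline summaries for hematology and "chemistry (also including prolactin and thyroid function parameters) for each treatment group and overall subjects at each study visit". The corresponding table in SAP 13.3 is Table 14.3.5.2, "Clinical Chemistry and Thyroid: Observed Results and Change from Baseline by Visit". Its shell in SAP 14.2 reads "Same as shell 14.3.5.1; Programming Note: Update Reference Listing to Listing 16.2.8.2", so it takes over the hematology layout: n, mean (SD), median, minimum and maximum, with an observed column and a change column at Visit 6. Nothing exempts a test that is run on only some subjects.

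SAP 6.1.7.1 defines change from baseline as "The value at the target time point minus the value at baseline". Under SAP 6.1.1 (Table 2), the laboratory baseline is the last non-missing value before the first dose. SAP 6.1.4 does not impute safety data, and SAP 6.1.5 sends unscheduled safety tests to listings only.

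Protocol 13.1.5.2 also promises shift tables (below, within or above normal range) for each analyte by arm and visit. SAP 9.2 and SAP Table 7 contain none. SAP Section 11, which lists departures from the planned analysis, does not mention dropping them; its only laboratory entry is that urinalysis will be listed rather than summarised.

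**The concern.** A mean change by arm is a fair description when everyone is measured at both times. A reflex test breaks that condition in two ways. Whether a Visit 6 value exists depends on that subject's own post-randomization TSH, so the observed mean describes a subset selected on an outcome, with low-TSH and high-TSH subjects averaged together. And a change value needs a trigger both before dosing and at Visit 6, so the change column leaves out the subjects whose thyroid function moved out of range during treatment.

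Changes in laboratory values are a named safety endpoint. At stake is whether the free T4 row says anything about treatment, and whether any planned table counts new thyroid abnormalities by arm.

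**Working it through.** **1. No figure to reproduce.** The plan states no number on this point. The main result is a matter of logic; only its size needs assumptions.

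**2. Which subjects can contribute.** Apply the reflex rule (Protocol 10.3.2.1.1) and the change definition (SAP 6.1.7.1) to each TSH pattern:

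| TSH before dosing | TSH at Visit 6 | Baseline free T4 | Visit 6 free T4 | Change value |
|---|---|---|---|---|
| In range | In range | No | No | No |
| In range | Out of range | No | Yes | No |
| Out of range | In range | Yes | No | No |
| Out of range | Out of range | Yes | Yes | Yes |

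Only the last pattern enters the change column. The second, the treatment-emergent pattern, never does. The baseline and Visit 6 observed means also rest on partly different subjects.

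**3. What counts as before dosing.** Thyroid tests are drawn at Screening and at Visit 2 (Protocol 10.2.1.1 and 10.2.2). SAP Table 2 ties the baseline to Visit 2, but the footnote to shell 14.3.5.1 says only last non-missing before the first dose. A Screening free T4 could therefore serve as baseline when TSH is back in range at Visit 2. A subject in range at both pre-dose visits still has no baseline free T4.

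**4. Size, for illustration.** Forty subjects randomized 1:1 gives about 20 per arm. The documents give no TSH rates, so these are assumed:

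- q, chance of a baseline free T4: 2.5% to 10%
- r, chance that TSH is still out of range at Visit 6, given it was out before: 50% to 80%
- e, chance that TSH is newly out of range at Visit 6, given it was in range before: 5% to 10%

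Expected number per arm with a change value = 20 × q × r. Chance that an arm has none = (1 − q × r)^20.

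| q | r | Expected with change | Chance of none |
|---|---|---|---|
| 2.5% | 50% | 0.25 | 78% |
| 2.5% | 80% | 0.40 | 67% |
| 5% | 50% | 0.50 | 60% |
| 5% | 80% | 0.80 | 44% |
| 10% | 50% | 1.00 | 36% |
| 10% | 80% | 1.60 | 19% |

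Expected emergent subjects per arm with a Visit 6 free T4 but no change value = 20 × (1 − q) × e. This runs from 20 × 0.90 × 0.05 = 0.90 to 20 × 0.975 × 0.10 = 1.95.

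Two features of the protocol move q in opposite directions. Two pre-dose draws raise it. The entry rule lowers it: where a Screening or Visit 2 result is clinically significant, "the subject should not be randomized at Visit 2".

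**The case against.** The case on the other side is mostly about reach, and much of it stands.

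- **The row is inferred.** The SAP never names free T4; the shell has a generic parameter line. The inference is reasonable, because SAP 9.2 speaks of thyroid parameters in the plural and the protocol has only two thyroid tests, but a programmer could produce TSH alone.
- **Emergent cases are not lost.** A reader might infer that the safety output hides new thyroid abnormalities. The documents do not support that. TSH is unconditional, so the planned test schedule gives it full observed and change rows. The emergent free T4 values themselves appear in the Visit 6 observed cell and in Listing 16.2.8.2 with out-of-range flags. Clinically significant chemistry results have their own listing (Table 14.3.4.2), and Protocol 10.3.2.1.3 requires clinically relevant laboratory changes to be reported as adverse events.
- **The row is unlikely to pass for a randomized comparison.** Safety analysis is descriptive, no laboratory test of significance is planned, and n is printed beside each mean.
- **Cancellation of opposite values is a weak argument.** It needs at least two values in an arm. If 5% of subjects had a Visit 6 free T4 (assumed), the chance of 0 or 1 value among 20 is 0.95^20 + 20 × 0.05 × 0.95^19 = 0.74; at 10% it is 0.39. The minimum and maximum would also show opposite extremes.

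What does not fall is the structural point. No choice of rates puts a subject who was in range at both pre-dose visits into the free T4 change column. Nor do listings replace a count by arm, and with the shift tables absent no planned laboratory table supplies one.

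**Conclusion.** The point holds in a narrow form. If free T4 is summarised as SAP 9.2 and Table 14.3.5.2 imply, its change column is restricted to subjects with out-of-range TSH at a pre-dose visit and again at Visit 6, and its Visit 6 mean to a TSH-selected subset. Neither describes an arm. This follows from the text and needs no numerical assumption beyond reading free T4 as one of the thyroid parameters.

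The consequence is minor. It concerns one sparse descriptive row in a 40-subject exploratory study; no subject-level data are lost and no efficacy result is affected. The expected 0.25 to 1.6 change values per arm, and the 19% to 78% chance of an empty cell, rest wholly on the assumed rates. The reason to act is that counts are valid where the mean and change are not, and the plan has no table of thyroid abnormality counts by arm.

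**What to change.** 1. In SAP 9.2 and the programming note for Table 14.3.5.2, limit the thyroid mean and change rows to TSH. Prolactin and the chemistry panel stay as planned.
2. For free T4, report by arm and visit the number of subjects tested, split by low or high TSH, and of these the number below, within and above range. Keep individual values in Listing 16.2.8.2.
3. Restore the Protocol 13.1.5.2 shift table, at least for TSH, so that newly out-of-range results are counted by arm. If the other analytes' shift tables are to stay out, record that in SAP Section 11.

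The cost is a sentence or two in SAP 9.2, a programming note, and a small amount of extra programming. No new data are needed. The free T4 table will be sparse.
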